2.2 Strategies for Family Supported PE

2.2A. Structure of Standard PE.

The PE treatment protocol includes education, imaginal exposure (repeatedly imagining and describing a trauma memory to the provider), in vivo exposure homework (exposure to trauma reminders in real life), and listening to audio recordings of Veterans' trauma accounts between sessions (imaginal exposure homework).⁵² The first sessions are largely educational. Imaginal exposure begins in Session 3. Due to the volume of material provided in Session 2, in VA care, it is frequently divided into two sessions: 2a (education on PTSD and avoidance; detailed rationale for in vivo exposure) and 2b (building a hierarchy of situations to approach at home; see Figure 2).

2.2B. Overview of Family Supported PE.

SPs will attend PE Sessions 1, 2a, and 2b; receive two check-in telephone calls; and be invited to elective in-person check-ins if indicated (see below). Dividing Session 2 into 2a and 2b allows for more time to discuss the content outlined below. Strategies for how to engage with families are drawn from existing evidence-based approaches. The goals for family engagement are to 1) educate SPs about how avoidance maintains PTSD, 2) facilitate discussion of how SPs encourage/discourage PE participation (accommodation), and 3) develop a plan, tailored to the Veteran-SP dyad, for how SPs will help Veterans participate (support plans). The VHA Blueprint for Excellence emphasizes patient-centered care,⁴⁰ which is both flexible and tailored.⁴⁴ Flexibility is essential to implementation of family involved treatments,⁷⁶ and to improving the clinical relevance of interventions.¹⁴ Consequently, inclusion/exclusion criteria only require Veterans bring a SP to Session 1 (if randomized), and discuss further SP attendance with their provider.

2.2C. Description of Strategies.

[figure not shown]

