3.0 Objectives

The objective of the proposed study is to evaluate the effectiveness of family support as a tool to improve Veterans' EBP adherence. We are proposing a randomized practical clinical trial employing an effectiveness-implementation Hybrid 1 design.⁴² This design will focus on external validity, flexibility, and liberal inclusiveness of the patient population.^{1;4;43;44} We will also identify potential facilitators and barriers of involving family in PE within VA. Our central hypothesis is that when families support Veterans' PE participation through attending PE's educational sessions (family supported PE), adherence will improve over PE as delivered in routine care.

Aim 1: To improve Veterans' adherence to PE through engaging families in care.

We hypothesize that when families support Veterans' PE participation through attending PE's initial educational sessions, Veterans' attendance to PE (H1a) and homework compliance (H1b) will improve, compared to PE as typically delivered.

Aim 2: To improve the clinical outcomes of Veterans receiving PE in routine care through engaging families in Veterans' treatment.

We hypothesize that family supported PE will be more effective than standard PE in reducing PTSD severity and comorbid problems (depression, quality of life, relationship functioning) from pre-to-posttreatment.

Aim 3: To examine barriers/facilitators of implementing family supported PE through a mixed-method, multi-stakeholder process evaluation¹⁰⁰ with patients, providers, and mental health leadership.

Exploratory Aim: To identify mechanisms underlying differences in adherence between treatment conditions.

We will explore if differences in adherence between family supported PE and standard PE are mediated by changes in key social influence variables, including family perceptions of treatment credibility, family support for Veterans' PE participation, and families' accommodation for PTSD symptoms.

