Consequently, providers will deliver both interventions. We will use block randomization within providers and within site, employing a completely randomized repeated measure block design (3 sites, 4 providers per site, 13 patients per provider). Randomization will be conducted by the study programmer, using blocks generated by the statistician. Participants will be informed of their randomization when they are contacted to schedule their first treatment session (after consenting and finalizing eligibility – discussed further below). Fidelity coding of session tapes will examine diffusion of family supported PE skills into standard PE. Veterans living 50 or more miles from the facility will be eligible for travel pay. Dyads with children will also be offered compensation for childcare, if necessary. Participants will be allowed \$10 an hour for childcare payments (e.g. 2 hour session plus 1 hour travel time equates to \$30 for childcare per session). Afterhours appointments will also be available at each study site.

5.1B. Providers and Training.

VA PE providers will provide the treatment. Across all sites, there are approximately 57 trained PE providers. Seventeen have expressed a desire to participate. All providers will attend a 2 day training in-person at the Minneapolis VA. Training will cover basic information on working with families, including confidentiality, managing conflict, and managing reports of relationship violence. It will provide instruction on educating families about accommodation, and facilitating constructive family communication through “I feel” statements,

5.1A. Randomization and Intervention Delivery.

Provider skill may differ, and randomizing providers to only one condition risks imbalance in skill of delivery across conditions. At the same time, when the providers are involved in both conditions, provider learning may diffuse into both conditions (i.e., skills for improving family support for PE influencing standard PE delivery). We anticipate the risk of the latter is limited as the treatment condition under study involves including families in care, which are excluded from the standard PE arm.

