Telephone check-ins: Following Session 2b, SPs will have two 15 minute telephone check-ins to make support plan adjustments. Call 1 will occur after the first *in vivo* exposures (Session 3), and Call 2 will occur two weeks later. If telephone check-ins reveal a) the family support plan is not going well, b) unresolved ambivalence about the treatment, or c) requests for more assistance in supporting Veterans' care, providers can add dyadic session(s), consistent with how this intervention would likely be delivered in good clinical practice. These sessions will discuss progress and the support plan. They can also be used to plan and facilitate trauma

disclosure if clinically indicated and desirable. Dyads expressing additional family or SP needs (e.g. mental health), will be provided site-specific referrals, including services for SPs, children, parenting training, and family/couple counseling as indicated.

After finishing treatment in both study conditions, Veterans will be referred back to their VA mental health care team in order to determine if they have any remaining mental health treatment needs. If they do not already have an established primary mental health care team or provider, they will be referred to the mental health care team at their VA facility to establish care and evaluate any remaining mental health treatment needs.

5.1E. Delivery by Telemedicine

We will recruit participants from CBOCs and offer to provide Prolonged Exposure treatment within the study using telemedicine. The telemedicine option would use VA approved electronic communication methods and information technology to provide Prolonged Exposure therapy to patients by study clinicians. This option would greatly benefit participants. Psychotherapy, including Prolonged Exposure (PE), is currently widely available within VA by telemedicine to improve Veteran access to care. The major benefit of telemedicine is that it eliminates travel that may be disruptive or costly to patients. Many individuals in need of specialized PTSD services live in geographically remote regions. Additionally, individuals needing mental health services may have physical limitations or disabilities. Providing Prolonged Exposure therapy to these individuals solely in medical centers can impose a tremendous financial, travel, or personal burden. Allowing a telemental health option for PE therapy will ease these burdens by making services more accessible to patients.

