Provider monitoring will mirror practices for potential future implementation and necessary for promoting good clinical practice (versus for a traditional efficacy trial). As study team members, providers will be trained in how to deliver the treatment consistent with the treatment protocol as an extension of how the PI would deliver it. To ensure the treatment is delivered properly, providers will have weekly consultation calls with study investigators, including the PI ([name], [name], [name], [name]). These meetings will include discussion of issues that arise with implementing the treatment protocol as intended. Providers will also record session attendance, rate subjects on homework compliance, and track out-of-session contact between providers and family members. Unlike an efficacy trial, providers will not be provided fidelity scores from reviewed sessions, as this unfeasible for large scale implementation. However, provider fidelity and competence in intervention strategies will be coded from audiotapes of sessions for use as covariates in study

analyses. Ten percent of providers' sessions where content varies between PE and family supported PE (1, 2a, 2b) will be randomly selected and coded using a fidelity checklist. Fidelity checklists will also evaluate potential contamination of family supported PE skills into standard PE. Study staff will be trained by [name] and [name] using checklists developed by the intervention team. Twenty-percent of sessions coded will be coded by a second expert coder ([name]), and reliability evaluated. If reliability is lower than benchmarks (i.e., kappa > .79), additional training of coders will ensue. Tapes will be re-coded and a new set of 20% will be coded by [name] until thresholds are achieved.

5.1H. Provider/Leadership Interviews.

Study therapists and 2 members of mental health leadership at each site will be invited to participate in semi-structured interviews conducted via telephone for Secondary Aim 2 (process evaluation). Clinic leadership at each site was consulted in the development of these study procedures for the grant application that we were awarded to support this project. They will be reminded by email a few months before formal recruitment efforts begin. Therapist interviews will last approximately 50 minutes and leadership interviews will last approximately 30 minutes. The interviews will be recorded and transcribed.

5.1I. Human Subjects Involvement and Characteristics.

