5.5 Study Evaluations

5.5A. Quantitative Data Collection (Aim 1, Aim 2, Exploratory Aim).

Except where indicated, data collection for the IC and RCT phase is identical. Aim 1 outcome variables will be obtained from Medical Records (attendance) and Provider Report (homework compliance). Aim 2 outcomes will be obtained from Baseline (week 0) and Posttreatment (16 weeks post-session 1) assessments of PTSD symptom severity, depression severity, quality of life, and relationship functioning. Aim 3 outcomes will be obtained from qualitative sources. Our Exploratory Aim outcomes will be obtained from Baseline, Posttreatment, and brief Weekly self-reports from Veterans and SPs. See below for measures.

5.5A.1 Aim 1. Aim 1 outcomes will be measured with methods drawn from Project HomeFront and our prior work coding session notes for PE/CPT treatment completion.⁵¹ PE attendance will be counted from review of Medical Records. Participants will have 'completed' PE when providers record they have successfully completed PE in a final session note. Providers will also be asked to log patient attendance and indicate the dates of attended sessions, missed sessions, and cancelled/rescheduled sessions. Homework compliance will be captured through patient observation by providers (Provider Report). Rating items were adapted from those used with Exposure and Response Prevention Therapy for Obsessive Compulsive Disorder (also a cognitive-behavioral exposure therapy).⁹³ Providers will also report on rates SP-provider contact weekly.

5.5A.2 Aim 2. Clinical outcomes for Aim 2 will be assessed through multiple forms (i.e., self-report and structured clinical interview), consistent with gold-standard methodology used in prior RCTs of PE and CPT. Baseline and posttreatment paper-and-pencil questionnaires will be completed by participants in both the RCT and IC phase of the study. Some participants in the IC phase will also receive structured interviews to allow the study team to implement all study procedures prior to beginning the RCT. IC participants will receive in-treatment assessments before sessions 2a and 2b to contribute to the intensive coaching and feedback providers receive for these early cases.

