For RCT phase, structured clinical interviews will take place at Baseline (week 0) and posttest (within 4 weeks of final session). Self reports/surveys will take place at Baseline (during week 0) and at posttreatment (during final session). For drop out Veteran participants, posttest surveys will be completed 16 weeks post-session 1 and the posttreatment clinical assessment will be done within 4 weeks of that posttest survey. For late treatment completers (i.e., treatment takes more than 16 weeks), all posttest surveys and post clinical interviews will be delayed but will be done no later than 24 weeks post-session 1.

For the IC phase, weekly surveys will be given for the first 2 weeks of treatment (session 2a, and 2b). For the RCT phase, weekly surveys will be given during weeks 2, 4, 5, 6, 8, 10 and 12 of treatment. For participants, the weekly surveys during week 2 and 8 will be lengthier and more thorough. All structured interviews (CAPS-5³ and SCID-5-CT)¹² will be administered by trained and supervised assessors who are blinded to condition. Assessors will be trained and supervised weekly by [name], a licensed clinical psychologist with expertise in conducting structured diagnostic clinical interviews and assessing and intervening with patients experiencing mental health crises. For mailed assessments, we will use CCDOR's well-established modified-Dillman protocol with repeated mailings and an incentive (incentive schedule described below).⁶ For surveys of Veterans with PTSD, our team's response rates

have ranged from 55% to 85%. Given the short interval between assessments, we will include a telephone call reminder and an offer telephone administration to optimize response rates.⁶

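### Homework compliance (H1b) is measured only by the unblinded treating provider, who by design has support-person contact in the family arm but only incidental contact in standard PE, so the arms may be rated on different information

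*Combined protocol and SAP*

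**What the plan says.** Protocol section 3.0 names two Aim 1 hypotheses: "attendance to PE (H1a) and homework compliance (H1b) will improve, compared to PE as typically delivered". Section 5.5A.1 gives the source of the second: "Homework compliance will be captured through patient observation by providers (Provider Report", with items adapted from an adherence scale for another exposure therapy. Section 5.1G assigns the task: "Providers will also record session attendance, rate subjects on homework compliance, and track out-of-session contact between providers and family members".

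The rater cannot be blinded. Section 5.1A states: "Consequently, providers will deliver both interventions". Blinding is described only for the structured interviews (CAPS-5 and SCID-5-CT), which section 5.5A.2 says "will be administered by trained and supervised assessors who are blinded to condition".

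On SP contact in the family arm, section 2.2B says "SPs will attend PE Sessions 1, 2a, and 2b; receive two check-in telephone calls", and section 5.1D adds "Following Session 2b, SPs will have two 15 minute telephone check-ins to make support plan adjustments". Section 5.1D also allows extra dyadic sessions on progress and the support plan. In standard PE (section 5.1C) providers do not solicit family attendance. If an SP makes contact, the provider acts as in routine practice, and the contact is recorded in weekly provider reports.

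**The concern.** A rating by someone who knows the arm can be shaped by expectation. Here the rater may also have an extra informant, mostly in one arm. An SP could vouch for a Veteran's homework and raise the rating, or disclose undone homework and lower it. Either would move the arm comparison without any change in behaviour.

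H1b is at stake, together with the section 5.6B2 models that use the same rating. Homework compliance is a fixed effect in the Aim 2 transition model, and it would carry the same problem into any adherence pathway built on it.

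**Working it through.** **1. The plan's own Aim 1 figure, and what it covers.** Inputs from section 5.6A1: a difference of 2 sessions, SD 4.45, 80% power, 78 per arm. Two-sided alpha of 0.05 is my assumption, since none is stated.

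n per arm = 2 × (1.960 + 0.842)² × (4.45 / 2)² = 2 × 7.849 × 4.951 = 77.7, rounded up to 78.

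The figure reproduces, with power of 80.1% at 78 per arm by the normal approximation. (The printed effect size of 0.43 differs from 2 / 4.45 = 0.449, but that has no bearing here.) The calculation is for attendance. No SD, target difference or power is given for homework ratings.

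**2. What the rater can know, by arm.**

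| | Family supported PE | Standard PE |
|---|---|---|
| Rater | Treating provider, knows the arm (5.1A, 5.1G) | Same |
| Stated basis of rating | Observation of the patient (5.5A.1) | Same |
| SP in sessions | Session 1; encouraged for 2a and 2b (5.1D) | Not solicited (5.1C) |
| Provider–SP calls | Two by design, after session 2b (5.1D) | Only if the SP initiates contact (5.1C) |
| Further dyadic sessions | At the provider's election (5.1D) | None described |

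**3. Could SP contact bear on homework?** Section 2.2A makes in vivo exposure a homework task. Section 5.1D places the first call after the first in vivo exposures (Session 3) and the second two weeks later, so both calls fall while exposure homework is under way. They concern the SP's plan for supporting adherence, and section 5.5A.5 gives assistance with homework as an example of SP support. It is therefore plausible that a call touches on whether homework was done. The documents do not say that it does.

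**4. Existing safeguards.**
- No section tells providers to use or to disregard what an SP says when rating.
- Tape coding (5.1G) covers 10% of sessions 1, 2a and 2b, for fidelity and contamination; homework is not mentioned.
- Provider–SP contact is logged (5.1C, 5.1G) and discussed as a covariate (5.5A.6); SP attendance is to be a covariate (5.3). Both arise after randomisation and are largely set by the arm. Adjusting for them cannot separate rating bias from a real effect and may absorb part of that effect.

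**5. Why no size follows.** If the Veteran-mean rating in one arm were shifted by b SD, the test statistic at 78 per arm would move by b / √(2/78) = b / 0.160. To find b one needs the shift per affected rating, the share of ratings affected, and the correlation of ratings within a Veteran. The documents give none of these, and the sign is open.

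**The case against.** The sponsor could answer that this is a practical trial with deliberately simple measures and limited quality assurance; that therapist ratings are an ordinary limitation of such trials; that the stated basis is observation of the patient; that the calls exist to adjust the support plan; and that SP contact is already tracked. The rating form and surveys sit in study materials outside these documents and may already name a source or include a Veteran homework item. Much of this stands. It makes the different-information point an inference and keeps the matter secondary. It does not supply a blinded or same-source measure of H1b, and a contact log records the exposure without removing its effect.

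Four stronger readings are tempting but not supported:
- A reader might infer that homework is reviewed with the SP present in sessions 2a and 2b. No section says so: they are described as education, hierarchy building and support planning, and section 5.1D places the first in vivo exposures at Session 3.
- A reader might infer that SP contact occurs only in the family arm. Section 5.1C allows it in standard PE, so the contrast is planned against incidental contact.
- A reader might want an inflated false-positive rate. Any such rate would rest on an invented shift.
- A reader might treat ratings from session 3 onward as free of SP influence. Both calls, and any added dyadic sessions, fall after that point, and the restriction also selects on reaching session 3.

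**Conclusion.** The concern holds in limited form. It is established that H1b has one described measure, that its rater knows the arm, that this rater has planned SP contact only in family supported PE, and that no blinded or same-source second measure is described. It is a reasonable inference, not a documented fact, that the information behind the ratings differs by arm. Size and direction are unknown.

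The scope is H1b and the secondary models that use homework compliance. Attendance is the primary outcome (5.6A) and is counted from medical records (5.5A.1), so the main result does not depend on this point. The conclusion assumes that the unseen rating form does not already restrict the source of the rating. A small change is worth making because H1b is a named Aim 1 hypothesis.

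**What to change.** 1. In section 5.5A.1 and on the rating form, instruct providers in both arms to rate homework at the start of each session from the Veteran's homework forms and own report only, disregarding anything learned from an SP.
2. Add a tick-box for any rating made with an SP present, or after SP contact since the last rating, linked to the contact log already kept.
3. If none is there, add one Veteran self-report homework item to the weekly surveys that both arms already receive (weeks 2, 4, 5, 6, 8, 10 and 12). Report it beside the provider rating. This equalises the informant; it does not blind, since Veterans know their arm.
4. In section 5.6B2, name the H1b model (only the model for sessions attended is written out) and repeat it without flagged ratings, labelled as sensitivity only.
5. State in the report that the homework rater was unblinded.

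The cost is one instruction, one tick-box, at most one survey item and one extra model run. The instruction reduces the problem but cannot make a provider forget what was heard. The sensitivity analysis uses fewer ratings, with losses expected mainly in the family arm, and selects on post-randomisation contact and attendance, so it cannot replace the main comparison.

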5.5A.6 Covariates. SP support for PE may better influence adherence with less SP distress, less family conflict, greater provider-SP contact, and certain demographic characteristics (e.g., gender, age, or race/ethnicity). SP distress will be assessed using the PROMIS Perceived Stress scale⁹⁸ and General Functioning scale of Family Assessment Device (FAD). Frequency of provider-SP contact will be assessed in weekly provider reports. Demographic variables such as race, gender, SP-Veteran relationship (e.g., spouse, parent, adult child), and frequency of SP-Veteran contact will also be assessed at Baseline.

5.5A.7 Qualtrics Online Surveys

Survey administration format will transition to Qualtrics FedRAMP electronic survey software accessed via the VA cloud. This transition will support data collection during the current COVID 19 directives. Our study sites have been ordered to "shelter in place" during the pandemic, making paper survey mailings unachievable. Paper surveys will still be available to those who need or request them, but we plan to use online surveys as our primary modality.

Qualtrics FedRAMP has been approved for use from the VA OIT Security standpoint (Authority to Operate or ATO). The ATO status is currently approved for 1 year and a full 3-year ATO is in the works. Qualtrics FedRAMP surveys will contain a study ID number, time of data entry and limited individually identifiable information. Within the VA firewall, the study team at the VA will create a custom- built tracking app that will track each participant's enrollment and study status. Data will be routinely extracted from Qualtrics FedRAMP in the VA cloud and stored on secure CCDOR servers, using SQL database connections. All data will be stored and utilized within secure CCDOR servers that are part of the Minneapolis VAMC network and which operate behind the VA firewall. All data is tracked using a SQL database, with a GUI-front end system that restricts access to only those with approval to study data.

Qualtrics FedRAMP surveys will contain minimal individually identifying information. The only identifying information will be information that is self-reported by the participants (e.g. name, phone, email, which is best method of contact). No sensitive data will be stored outside of the VA protected environment. Once data are transferred for data analysis, data will be maintained on password-protected VA computers in the VA environment and on secure VA servers.

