5.6B2. Aims 1 and 2. After completing the above steps, we will test our hypothesis for Aim 1 using generalized linear mixed models. The number of sessions attended, within the assumed and appropriate fitted distribution, will be modeled with treatment and site as fixed effects and a random provider effect (clustering by provider). Analyses for Aim 2 will similarly use mixed models to examine differences between conditions on PCL-5 scores over time, modeling the treatment, time, and treatment by time effects. Secondary analyses will examine CAPS-5 scores and loss of diagnosis on the CAPS-5 (both PTSD diagnosis and subclinical PTSD diagnosis) to facilitate comparisons with existing and ongoing research on treatments for PTSD. We will also examine differences between conditions on PHQ-9, WHO-QOL, QRI, and CSQ-8 scores.

Analyses will follow the same general approach as Aim 1, with some exceptions. First, some indices are dichotomous (i.e., presence or absence of PTSD or subclinical PTSD diagnosis). Models will be fit using appropriate distribution and link functions (i.e. for binomial distribution and logit links for PTSD diagnosis; whereas mean group differences might fit a normal distribution). Second, unlike Aim 1, which relies on administrative data, Aim 2 outcomes rely on

self-report data, where some attrition is inevitable. Analyses will include examining group differences using available data, as well as analyses employing imputation as described above. To study the time-dependence of clinical outcomes, we will model the first-order transition probabilities of Markov chains (under treatment and control) with auto regressive random intercepts, random slope (provider), and fixed effects for treatment, site, sessions attended, and homework compliance. Lastly, we will explore indirect pathways from family supported PE to improved treatment outcomes through greater adherence (e.g., treatment condition → session attendance → PTSD symptoms), using approaches for testing indirect effects described below.

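### Section 5.1G makes post-randomisation fidelity scores covariates without saying in which analyses or at what level, and this is not reconciled with the intent-to-treat models in 5.6B

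*Combined protocol and SAP*

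**What the plan says.** Section 5.1G states that "provider fidelity and competence in intervention strategies will be coded from audiotapes of sessions for use as covariates in study" analyses. On sampling it says: "Ten percent of providers' sessions where content varies between PE and family supported PE (1, 2a, 2b) will be randomly selected", to be coded with a fidelity checklist. It adds: "Fidelity checklists will also evaluate potential contamination of family supported PE skills into standard PE". It does not say which analyses are meant, whether the score is per session, Veteran, provider or provider within arm, whether each arm is scored against its own protocol, or what happens to Veterans with no coded session.

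The analysis section does not repeat the rule. Section 5.6B1 promises intent-to-treat, adjusts for baseline characteristics found to differ between arms, and plans both a complete-case analysis and an analysis of five data sets with missing covariates imputed. In section 5.6B2 the Aim 1 attendance model has fixed effects for treatment and site and a random effect for provider. The Aim 2 PCL-5 model has treatment, time and their interaction. Neither names fidelity.

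The design matters here. Section 5.1A says "Consequently, providers will deliver both interventions" and "We will use block randomization within providers and within site".

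Two related variables are handled in a similar way. Section 5.5A.6, headed Covariates, includes provider-SP contact: "Frequency of provider-SP contact will be assessed in weekly provider reports". Section 5.3 makes SP attendance a covariate in unspecified analyses.

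**The concern.** Fidelity and competence are observed in treatment sessions, after assignment. Sessions 1, 2a and 2b are coded because that is where the two arms differ in content. If the checklist scores family strategies, and the score can differ between arms within a provider, it records how much of the randomised treatment was delivered. With that score in the model, the treatment coefficient describes being in the family arm with delivery of the family strategies held fixed. That is not the intent-to-treat effect that 5.6B1 promises. Two things could follow: loss of precision, because score and arm are correlated, and shrinkage of the estimate, because part of the true effect is credited to the score.

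The wording leaves room for this. The plan already places post-randomisation variables beside treatment elsewhere: the Markov transition model in 5.6B2 includes sessions attended and homework compliance. The absence of fidelity from the written Aim 1 model does not rule it out either, since that model also omits the imbalance covariates that 5.6B1 says will be added. If the choice waits until data are in hand, adjustment can be selective.

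**Working it through.** **Inputs from the plan.** 78 Veterans per arm, 156 in all; SD of sessions attended 4.45; target difference 2 sessions; 80% power (5.6A and 5.6A1). 12 providers with 13 Veterans each, both arms within every provider (5.1A). 10% of sessions 1, 2a and 2b coded (5.1G). **Assumed, because not stated:** two-sided alpha of 0.05; the correlation r between score and arm; the share of the effect that passes through the score.

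**1. The plan's own figure.** n per arm = 2 × (1.96 + 0.8416)² × 4.45² / 2² = 77.7, so 78. Power at 78 per arm is 80.1%. The plan's number reproduces from 2 sessions and SD 4.45. (2/4.45 is 0.449, not the printed 0.43; this does not affect the present point.)

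**2. How much would be coded.** 156 × 3 = 468 eligible sessions if all are attended. 10% is about 47, or 47/12 = 3.9 per provider and about 2 per provider per arm. The chance that a Veteran has at least one coded session is 1 − 0.9³ = 27.1% (27.3% for a simple random draw of 47 from 468), which is about 42 Veterans. The ceiling is 47/156 = 30%. A Veteran-level score would therefore be missing for about 73%, and for at least 70%.

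**3. Complete-case power with a Veteran-level score.** SE = 4.45 × √(4/42) = 1.37, and 2/1.37 = 1.46, giving power of about 31%. This assumes an even split between arms and is before any loss from correlation with arm. The imputed analysis would keep all 156 but would fill in at least 70% of the scores. A Veteran who never attends session 1, a case that 5.1C provides for, can have no tape from it, so the complete cases are also selected on attendance, the primary outcome.

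**4. Loss of precision if every Veteran had a score and none of the effect passed through it.** The variance of the treatment estimate is multiplied by 1/(1 − r²):

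| r (assumed) | Variance factor | Power for 2 sessions |
|---|---|---|
| 0 | 1.00 | 80% |
| 0.5 | 1.33 | 68% |
| 0.7 | 1.96 | 52% |
| 0.8 | 2.78 | 39% |
| 0.9 | 5.26 | 23% |
| 0.95 | 10.26 | 14% |

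**5. Shrinkage under mediation.** Simulation with 2000 runs, 12 providers × 13 Veterans, arm blocked within provider, true effect 2 sessions, Veteran-level score:

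- Half of the effect through the score: the estimate falls from about 2.0 to 0.98; power is about 16% at r = 0.7 and 9% at r = 0.9.
- All of the effect through the score: the estimate is about 0 and the rejection rate about 5% at either r.

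**6. One score per provider.** In the same simulation the estimate is 1.98 with and without the score, and power is about 79% both ways. Every provider treats both arms in near-equal numbers, so a provider-level value is almost unrelated to arm.

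**7. Provider-SP contact.** Section 5.1D schedules two telephone check-ins with the SP in the family arm. Section 5.1C schedules no SP contact in standard PE. Even if only out-of-session contact is counted, the variable is raised by assignment.

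**The case against.** The strongest reply is that the harmful reading is not the only one, and perhaps not the most natural. Section 5.1G speaks of provider fidelity and samples providers' sessions. With 10% coding, a Veteran-level covariate is hardly workable, so a provider-level score is at least as plausible, and step 6 shows that it does no damage. The checklist content is not given either; if each arm is scored against its own protocol, the score need not follow arm. The written Aim 1 and PCL-5 models leave fidelity out, 5.6B1 is clear on intent-to-treat, and 5.5B assigns fidelity monitoring to the Aim 3 process evaluation. On provider-SP contact, the rationale in 5.5A.6 is effect modification, and nothing there puts it in an Aim 1 or Aim 2 model.

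All of this stands, and it limits the point. A reader might infer that the fidelity score is nearly a copy of treatment arm and that the primary analysis, as planned, would make a working intervention look null. The documents do not support that: they give neither the level of the score nor the checklist content, and the primary model as written has no fidelity term. The near-zero estimate in step 5 needs both a score for every Veteran and complete mediation. The 31% figure applies to the complete-case analysis alone; 5.6B1 also plans imputation.

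The reply does not remove the instruction itself. Section 5.1G says that the scores are for use as covariates and excludes no analysis. The harmless reading gains essentially nothing, while the other readings conflict with 5.6B1.

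**Conclusion.** The point holds as an unreconciled and unrestricted covariate rule, not as a defect written into the primary model. The harm is conditional on a score of family strategies, at session, Veteran or provider-by-arm level, entering an Aim 1 or Aim 2 treatment model. Under that condition, power for two sessions falls from 80% to about 68% at r = 0.5 and about 23% at r = 0.9 with no mediation, and the estimate shrinks towards zero in proportion to any mediation. The correlations and mediated shares are assumptions shown as ranges. The coverage figure, about 27% of Veterans, follows from the 10% sampling rule and assumes that all three sessions are attended; missed sessions would lower it. The point is worth settling before analysis, because it concerns what the treatment coefficient means and the correction is easy.

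**What to change.** In 5.1G, replace the clause that makes the scores covariates in study analyses with a statement along these lines: fidelity and competence are reported by arm and used only in the process evaluation or in exploratory analyses, for example as predictors within the family supported PE arm; they do not enter the Aim 1 or Aim 2 treatment-effect models. State the level at which the score is formed and how Veterans without a coded session are handled in any exploratory use.

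In 5.5A.6, state that provider-SP contact is measured after randomisation and is likewise limited to exploratory models. The same sentence can cover the SP-attendance covariate in 5.3; correcting that one alone would leave 5.1G and 5.5A.6 as they are.

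The cost is wording only. Coding, data collection and the models in 5.6B2 are unchanged, and the exploratory use of fidelity is kept.
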